10.1 Extent of exposure

The duration of exposure and time at risk will be summarized for the Double-Blind Period and the entire treatment period. For the entire treatment period the duration of exposure and time at risk will be calculated for bimekizumab 160mg and 160mg with loading dose, bimekizumab 320mg, and all bimekizumab. The calculation of exposure duration and time at risk for the all bimekizumab group is different from that of the other two groups. For all bimekizumab the duration of exposure and time at risk will include the time a subject received any dose of bimekizumab (including 16mg) while for the other two treatment groups only the time a subject received 160mg, 160mg with loading dose, or 320mg will be included into the calculation.

Duration of exposure Double-Blind Period

The duration of exposure (in days) during the Double-Blind Period will be calculated as:

$$\begin{aligned} \text{Duration of exposure} &= \text{Date of last injection (double - blind period)} \\ &- \text{Date of first injection (double - blind period)} + 28 \end{aligned} \quad (16)$$

28 days refer to one half-life of bimekizumab.

Note: If the date of last injection (Double-Blind Period) + 28 extends to a date beyond the date of first injection (Dose-Blind Period), then this calculation reverts to

$$\begin{aligned} \text{Duration of exposure} &= \text{Date of first injection (dose - blind period)} \\ &- \text{Date of first injection (double - blind period)} + 1 \end{aligned} \quad (17)$$

For subjects who die during the Double-Blind Period, then this calculation reverts to:

$$\begin{aligned} \text{Duration of exposure} &= \text{Date of death} - \text{Date of first injection (double} \\ &- \text{blind Period)} + 1 \end{aligned} \quad (18)$$

Duration of exposure entire treatment period

For subjects who do not switch study treatments, who receive bimekizumab 160mg with loading dose at Baseline, or who receive bimekizumab 16mg and will be summarized under all bimekizumab group:

$$\begin{aligned} \textit{Duration of exposure} \\ = \textit{Date of last injection} - \textit{Date of first injection} + 28 \end{aligned} \quad (19)$$

Note: If the date of last injection +28 extends to a date beyond the final visit date (not including SFU), then this calculation reverts to:

$$\begin{aligned} \textit{Duration of exposure} \\ = \textit{Date of last visit (not including SFU)} \\ - \textit{Date of first injection} + 1 \end{aligned} \quad (20)$$

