For subjects who die, then this calculation reverts to:

$$\textit{Duration of exposure} = \textit{Date of death} - \textit{Date of first injection} + 1 \quad (21)$$

For subjects who receive Placebo or bimekizumab 16mg in the Double-Blind Period and will be summarized under their Dose-Blind treatment in the overall table group bimekizumab 160mg or 320mg, or subjects who received Placebo and will be summarized in the overall table under their Dose-Blind treatment:

$$\begin{aligned} \textit{Duration of exposure} \\ = \textit{Date of last injection} - \textit{Date of first injection (dose} \\ - \textit{blind period)} + 28 \end{aligned} \quad (22)$$

Note: If the date of last dose +28 extends to a date beyond the final visit date (not including SFU), then this calculation reverts to:

$$\begin{aligned} \textit{Duration of exposure} \\ = \textit{Date of last visit (not including SFU)} \\ - \textit{Date of first injection (dose - blind period)} + 1 \end{aligned} \quad (23)$$

For subjects who die during the Dose-Blind Period, then this calculation reverts to:

$$\begin{aligned} \textit{Duration of exposure} \\ = \textit{Date of death} - \textit{Date of first injection (dose} \\ - \textit{blind period)} + 1 \end{aligned} \quad (24)$$

The sum over all duration of exposure (in years) will be calculated for the total subject-years of duration of exposure.

The duration of exposure will be summarized by treatment group using descriptive statistics. A by-subject listing of date of first and last dose in Double-Blind Period, the date of first and last dose in Dose-Blind Period and the duration of exposure during Double-Blind Period and under bimekizumab treatment (any dose of bimekizumab) will be performed.

Time at risk Double-Blind Period

For subjects who complete the final visit of the Double-Blind Period and continue to the Dose-Blind Period:

$$\begin{aligned} \text{Time at risk} &= \text{Date of first injection (dose – blind period)} \\ &\quad - \text{Date of first injection (double – blind period)} + 1 \end{aligned} \quad (25)$$

For subjects who discontinue on or prior to the final visit of the Double-Blind Period, use the minimum of the following:

$$\begin{aligned} &\text{Date of last injection (double – blind period)} \\ &\quad - \text{Date of first injection (double – blind period)} + 140 \end{aligned} \quad (26)$$

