$$\begin{aligned} &\text{Date of final contact} - \text{Date of first injection (double – blind period)} \\ &\quad + 1 \end{aligned} \quad (27)$$

$$\begin{aligned} &\text{Date of last visit (not including SFU)} - \text{Date of first injection (double} \\ &\quad - \text{blind period)} + 1 \end{aligned} \quad (28)$$

where 140 days refers to 5*half-life of bimekizumab.

For subjects who die during the Double-Blind Period, then this calculation reverts to:

$$\text{Date of death} - \text{Date of first injection (double – blind period)} + 1 \quad (29)$$

Time at risk entire treatment period

For subjects who do not switch study treatments, who receive bimekizumab 160mg with loading dose at Baseline, or who receive bimekizumab 16mg and will be summarized under all bimekizumab group:

For subjects who complete the Dose-Blind Period and enter the extension study:

$$\text{Time at risk} = \text{Date of Visit 16 (Week 48)} - \text{Date of first injection} + 1 \quad (30)$$

For subjects who die prior to the final visit:

$$\text{Time at risk} = \text{Date of death} - \text{Date of first injection} + 1 \quad (31)$$

For all other subjects, use the minimum of the following:

$$\text{Date of last injection} - \text{Date of first injection} + 140 \quad (32)$$

$$\text{Date of final contact} - \text{Date of first injection} + 1 \quad (33)$$

For subjects who receive Placebo or bimekizumab 16mg in the Double-Blind Period and will be summarized under their Dose-Blind treatment in the overall table with bimekizumab 160mg or 320mg, or for subjects who receive Placebo and will be summarized in the overall table under their Dose-Blind treatment:

For subjects who complete the Dose-Blind Period and enter the extension study:

$$\begin{aligned} \text{Time at risk} &= \text{Date of Visit 16 (Week 48)} \\ &\quad - \text{Date of first injection (dose - blind period)} + 1 \end{aligned} \quad (34)$$

For subjects who die during the Dose-Blind Period:

$$\begin{aligned} \text{Time at risk} &= \text{Date of death} - \text{Date of first injection (dose} \\ &\quad - \text{blind period)} + 1 \end{aligned} \quad (35)$$

For all other subjects, use the minimum of the following:

$$\begin{aligned} &\text{Date of last injection} - \text{Date of first injection (dose - blind period)} \\ &\quad + 140 \end{aligned} \quad (36)$$

$$\begin{aligned} &\text{Date of final contact} - \text{Date of first injection (dose - blind period)} \\ &\quad + 1 \end{aligned} \quad (37)$$

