The duration of exposure and time at risk will be summarized for the Double-Blind Period and the entire treatment period. For the entire treatment period the duration of exposure and time at risk will be calculated for bimekizumab 160mg and 160mg with loading dose, bimekizumab 320mg, and all bimekizumab. The calculation of exposure duration and time at risk for the all bimekizumab group is different from that of the other two groups. For all bimekizumab the duration of exposure and time at risk will include the time a subject

received any dose of bimekizumab (including 16mg) while for the other two treatment groups only the time a subject received 160mg, 160mg with loading dose, or 320mg will be included into the calculation.

Duration of exposure Double-Blind Period

The duration of exposure (in days) during the Double-Blind Period will be calculated as:

$$\begin{aligned} \text{Duration of exposure} &= \text{Date of last injection (double – blind period)} && (16) \\ &- \text{Date of first injection (double – blind period)} + 28 \end{aligned}$$

28 days refer to one half-life of bimekizumab.

Note: If the date of last injection (Double-Blind Period) + 28 extends to a date beyond the date of first injection (Dose-Blind Period), then this calculation reverts to

$$\begin{aligned} \text{Duration of exposure} &= \text{Date of first injection (dose – blind period)} && (17) \\ &- \text{Date of first injection (double – blind period)} + 1 \end{aligned}$$

For subjects who die during the Double-Blind Period, then this calculation reverts to:

$$\begin{aligned} \text{Duration of exposure} &= \text{Date of death} - \text{Date of first injection (double} && (18) \\ &- \text{blind Period)} + 1 \end{aligned}$$

Duration of exposure entire treatment period

For subjects who do not switch study treatments, who receive bimekizumab 160mg with loading dose at Baseline, or who receive bimekizumab 16mg and will be summarized under all bimekizumab group:

$$\begin{aligned} \text{Duration of exposure} &= \text{Date of last injection} - \text{Date of first injection} + 28 && (19) \end{aligned}$$

Note: If the date of last injection +28 extends to a date beyond the final visit date (not including SFU), then this calculation reverts to:

$$\begin{aligned} \text{Duration of exposure} &= \text{Date of last visit (not including SFU)} && (20) \\ &- \text{Date of first injection} + 1 \end{aligned}$$

For subjects who die, then this calculation reverts to:

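### Double-Blind exposure (SAP 10.1, equation 16) lacks the last-visit limit used in the related formulas, so some early leavers get more exposure in 12 weeks than in the whole study

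*SAP*

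**What the plan says.** All of the rules are in SAP 10.1, as current text; the Amendment 5 log in 13.5.2 repeats them.

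- **Double-Blind exposure.** Equation 16 is last injection − first injection + 28. The SAP explains the added days: "28 days refer to one half-life of bimekizumab". There are two exceptions. "If the date of last injection (Double-Blind Period) + 28 extends to a date beyond the date of first injection (Dose-Blind Period", equation 17 counts only to that Dose-Blind injection. Equation 18 is introduced by "For subjects who die during the Double-Blind Period, then this calculation reverts to" and counts to the date of death.
- **Entire-period exposure.** Equation 19 has the same form, but with a last-visit limit: "If the date of last injection +28 extends to a date beyond the final visit date (not including SFU", equation 20 counts only to that visit. Equations 22 and 23 do the same for rerandomized subjects.
- **Double-Blind time at risk.** "For subjects who discontinue on or prior to the final visit of the Double-Blind Period, use the minimum of the following": equations 26, 27 and 28. Equation 28 runs to the "Date of last visit (not including SFU", meaning the safety follow-up visit is left out.
- **Deaths, entire period.** "For subjects who die, then this calculation reverts to" death − first injection + 1 (equation 21), with no restriction on when the death occurs. Equation 24, for rerandomized subjects, covers only deaths during the Dose-Blind Period, which SAP 3.2.2 ends at the Week 48 visit.

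SAP 10.1 also sums exposure to total subject-years and lists Double-Blind exposure and any-bimekizumab exposure together for each subject.

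**The concern.** A subject who leaves alive before Week 12 has neither a Dose-Blind injection nor a date of death, so nothing shortens equation 16 and the full 28 days always count. The other two formulas that describe the same subject over the same time stop at the last visit. Double-Blind exposure can then be longer than entire-period exposure, so the part exceeds the whole. It can also be longer than Double-Blind time at risk. No other section of the SAP supplies the missing limit. The by-subject listing would show the first contradiction directly, and the subject-year totals would carry it.

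**Working it through.** **Inputs.** First injection F = Day 1. Double-Blind injections at Baseline, Week 4 and Week 8 (SAP 2.3), so last injection L is Day 1, 29 or 57. V is the last visit other than safety follow-up; for a subject who withdraws from the study this is the early termination visit (Protocol 5.1.2). There is no Dose-Blind injection. Final contact is on or after V. The SAP states no figure to reproduce here, so the formulas are applied as written.

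**One subject: L = 57, V = 64.**
- Equation 16: 57 − 1 + 28 = 84 days.
- Equations 19 and 20: 57 + 28 = 85, which is past 64, so 64 − 1 + 1 = 64 days.
- Equations 26 to 28: the minimum of 57 − 1 + 140 = 196, final contact (at least 64) and 64 − 1 + 1 = 64, so 64 days.

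**General form.** When V is before L + 28, the excess is (L − F + 28) − (V − F + 1) = 27 − (V − L). It is at most 27 days, when the dosing visit is the last visit, and zero once V is 27 or more days after L.

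| L | V | Double-Blind exposure | Entire-period exposure | Double-Blind time at risk | Excess over entire-period exposure |
|---|---|---|---|---|---|
| 1 | 8 | 28 | 8 | 8 | 20 |
| 29 | 36 | 56 | 36 | 36 | 20 |
| 57 | 57 | 84 | 57 | 57 | 27 |
| 57 | 71 | 84 | 71 | 71 | 13 |
| 57 | 78 | 84 | 78 | 78 | 6 |
| 57 | 84 | 84 | 84 | 84 | 0 |

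**Return at Week 12.** Protocol 6.3 asks subjects who stop treatment before Week 12 under its criteria 4 to 10 to come back for that visit. At V = 85 Double-Blind and entire-period exposure agree: 28 and 28, 56 and 56, 84 and 84 for L = 1, 29 and 57. A return three days early (V = 82) after a Day 57 injection leaves 84 against 82.

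**With the last-visit limit added to equation 16.** Double-Blind exposure equals entire-period exposure in every row above. A completer with the first Dose-Blind injection on Day 85 keeps 84 days.

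**Deaths.** Equation 21 has no 28-day limit: last injection Day 57 and death on Day 157 gives 157 − 1 + 1 = 157 days, against 57 − 1 + 28 = 84. For the contrast by switching status, take last injection Day 309 (Week 44), Week 48 visit Day 337 and death in follow-up on Day 400:
- Non-switcher: equation 21 gives 400 − 1 + 1 = 400 days; without the death, equation 19 gives 309 − 1 + 28 = 336. The death adds 64 days.
- Rerandomized, first Dose-Blind injection Day 85: equation 24 does not apply after Week 48, so equation 22 gives 309 − 85 + 28 = 252 days. The death adds nothing.

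**The case against.** The best defence is pharmacological. The 28 days stand for a half-life, and a subject injected on Day 57 and last seen on Day 64 still carries drug. On that view 84 days is reasonable and the 64 from equation 20 is the understatement. As a choice of convention this is fair, and the documents do not say which convention is better in principle. It does not rescue the plan, because equations 20 and 23 cut the same 28-day tail at the last visit. The SAP uses both conventions for one subject, and they cannot both stand.

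The second defence is that the two summaries are not laid out to reconcile. The Double-Blind summary is by randomized arm and includes placebo; the entire-period summary pools 160mg with and without loading dose, shows 320mg and all bimekizumab, and leaves out placebo time. That holds for table totals. It does not hold for the by-subject listing, where the two exposure figures stand together, or for exposure against time at risk within the Double-Blind Period.

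Three stronger readings go too far. A reader might infer that every early leaver is affected; the 27-day condition and the Week 12 return rule that out. A reader might infer that adverse event rates are distorted; SAP 10.2 and 10.2.2 calculate the exposure-adjusted rates only for the complete treatment period, from time at risk or time to first event, so Double-Blind exposure enters none of them. A reader might infer that any death in follow-up is treated differently by switching status; for a rerandomized subject who left early and had no Week 48 visit, equation 24 may still apply, so the difference is clear only for deaths after Week 48.

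**Conclusion.** The inconsistency is real and minor. It concerns subjects with no Dose-Blind injection whose last visit before safety follow-up is less than 27 days after the last injection. For them Double-Blind exposure exceeds Double-Blind time at risk by 27 minus that gap. Bimekizumab subjects have the same excess over entire-period exposure (for 16mg, in the all-bimekizumab group only). Placebo leavers have no entire-period figure, so only the mismatch with time at risk applies to them.

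The per-subject result follows from the formulas alone. Arm-level size depends on assumptions that are not in the documents. If 2 to 6 of 40 subjects leave, with the last visit 7 to 21 days after the last injection and no return at Week 12, the excess is 2 × 6 = 12 to 6 × 20 = 120 days, or 0.4% to 3.6% of 40 × 84 = 3,360 days. This is a scenario, not an estimate, and the difference between arms would depend on visit timing as well as on the number of leavers.

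Only descriptive exposure summaries, subject-year totals and the listing are touched. The death rules are a secondary and rare fault of the same kind.

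**What to change.** In SAP 10.1, add one rule to equation 16: for subjects who do not enter the Dose-Blind Period, if last injection + 28 is after the last visit (not counting safety follow-up), use last visit − first injection + 1, as equations 20 and 23 already do.

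For deaths, use in equations 18, 21 and 24 the smaller of death − first injection + 1 and last injection − first injection + 28, with the first injection of the period concerned, and state it without regard to when the death occurs. In the Day 400 example this gives 336 days for the non-switcher and 252 for the rerandomized subject (the smaller of 400 − 85 + 1 = 316 and 252), so the death no longer adds exposure to either.

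The cost is one added rule, three amended death formulas and the matching change in the exposure programming. Stated Double-Blind exposure becomes slightly smaller.
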